#### **Adverse events**

All information obtained on adverse events will be displayed by treatment group, cohort and participant.

The number (and percentage) of participants with treatment emergent adverse events (events started after the first dose of study medication or events present prior to start of double-blind

treatment but increased in severity based on preferred term) will be summarized in the following ways:

- by treatment, primary system organ class and preferred term.
- by treatment, primary system organ class, preferred term and maximum severity.
- by treatment, Standardized MedDRA Query (SMQ) and preferred term.

A participant with multiple adverse events within a primary system organ class is only counted once towards the total of the primary system organ class.

### **Vital signs**

All vital signs data will be listed by treatment group, cohort, participant, and visit/time and if ranges are available, abnormalities (and relevant orthostatic changes) will be flagged. Summary statistics will be provided by treatment, cohort and visit/time.

### **ECG**

1. PR, QRS, QT, QTcF, and RR intervals will be obtained from 12-lead ECGs for each participant during the study. ECG data will be read and interpreted locally for safety. In addition, 12-lead ECGs may be read centrally.
2. Categorical Analysis of QT/QTc interval data based on the number of participants meeting or exceeding predefined limits in terms of absolute QT/QTc intervals or changes from baseline will be presented. In addition, a listing of these participants will be produced (by treatment group).

QTcF and QRS duration will be examined separately between individuals with and without a complete bundle branch block.

All ECG data will be listed by treatment group, cohort, participant, and visit/time, and abnormalities will be flagged. Summary statistics will be provided by treatment, cohort and visit/time.

### **Clinical laboratory evaluations**

All laboratory data will be listed by treatment group, cohort, participant, and visit/time and if normal ranges are available abnormalities will be flagged. Summary statistics will be provided by treatment, cohort and visit/time. Shift tables using the low/normal/high/ (low and high) classification will be used to compare baseline to the worst on-treatment value.

#### **12.5.2 Pharmacokinetics**

Commercially Confidential Information

Commercially Confidential Information

**Table 12-1 Non-compartmental pharmacokinetic parameters**

AUC last	The AUC from time zero to the last measurable concentration sampling time (t last ) (mass x time x volume  )
C max	The maximum (peak) observed plasma drug concentration after single dose administration (mass x volume  )
T max	The time to reach maximum (peak) plasma drug concentration after single dose administration (time)

**12.5.3 PK/PD relationships**

Commercially Confidential Information

**12.6 Analysis of exploratory endpoints**

Commercially Confidential Information

Commercially Confidential Information

## **12.7 Interim analyses**

Commercially Confidential Information

## **12.8 Sample size calculation**

### **12.8.1 Primary endpoint(s)**

Commercially Confidential Information

## **13 Ethical considerations and administrative procedures**

### **13.1 Regulatory and ethical compliance**

This clinical study was designed and shall be implemented, executed and reported in accordance with the ICH Harmonized Tripartite Guidelines for Good Clinical Practice, with applicable local regulations (including European Directive 2001/20/EC, US CFR 21), and with the ethical principles laid down in the Declaration of Helsinki.

### **13.2 Responsibilities of the investigator and IRB/IEC**

Before initiating a trial, the Investigator/institution must obtain approval/favorable opinion from the Institutional Review Board/Independent Ethics Committee (IRB/IEC) for the trial protocol, written informed consent form, consent form updates, participant recruitment procedures (e.g., advertisements) and any other written information to be provided to participants. Prior to study start, the Investigator is required to sign a protocol signature page confirming his/her agreement to conduct the study in accordance with these documents and all of the instructions and procedures found in this protocol and to give access to all relevant data and records to Novartis Institutes for BioMedical Research monitors, auditors, Novartis Institutes for BioMedical Research Quality Assurance representatives, designated agents of Novartis Institutes for BioMedical Research, IRBs/IECs, and regulatory authorities as required. If an inspection of the clinical site is requested by a regulatory authority, the Investigator must inform Novartis Institutes for BioMedical Research immediately that this request has been made.

### **13.3 Publication of study protocol and results**

The protocol will be registered in a publicly accessible database such as [clinicaltrials.gov](http://clinicaltrials.gov) and as required in EudraCT. In addition, after study completion (defined as last patient last visit) and finalization of the study report the results of this trial will be submitted for publication and posted in a publicly accessible database of clinical trial results, such as the Novartis clinical trial results website and all required Health Authority websites (e.g., [Clinicaltrials.gov](http://Clinicaltrials.gov), [EudraCT](http://EudraCT) etc.).

For details on the Novartis Institutes for BioMedical Research publication policy including authorship criteria, please refer to the Novartis Institutes for BioMedical Research publication policy training materials.

### **13.4 Quality Control and Quality Assurance**

Novartis Institutes for BioMedical Research maintains a robust Quality Management System (QMS) that includes all activities involved in quality assurance and quality control, to ensure compliance with written Standard Operating Procedures as well as applicable global/local GCP regulations and ICH Guidelines.

Audits of investigator sites, vendors, and Novartis Institutes for BioMedical Research systems are performed by auditors, independent from those involved in conducting, monitoring or performing quality control of the clinical trial. The clinical audit process uses a knowledge/risk based approach.

Audits are conducted to assess GCP compliance with global and local regulatory requirements, protocols and internal SOPs, and are performed according to written Novartis Institutes for BioMedical Research processes.

### **13.5 Participant Engagement**

The following participant engagement initiatives are included in this study and will be provided, as available, for distribution to study participants at the timepoints indicated. If compliance is impacted by cultural norms or local laws and regulations, sites may discuss modifications to these requirements with Novartis.

- Thank You letter – at beginning and end of study participation
- Plain language trial summary – after CSR publication
- Individual treatment information – after CSR publication

## **14 Protocol adherence**

This protocol defines the study objectives, the study procedures and the data to be collected on study participants. Additional assessments required to ensure safety of participants should be administered as deemed necessary on a case by case basis. Under no circumstances including incidental collection is an Investigator allowed to collect additional data or conduct any additional procedures for any purpose involving any investigational drugs under the protocol, other than the purpose of the study. If despite this interdiction prohibition, data, information, observation would be incidentally collected, the investigator shall immediately disclose it to Novartis and not use it for any purpose other than the study, except for the appropriate monitoring on study participants.

Investigators ascertain they will apply due diligence to avoid protocol deviations. If an Investigator feels a protocol deviation would improve the conduct of the study this must be considered a protocol amendment, and unless such an amendment is agreed upon by Novartis Institutes for BioMedical Research and approved by the IRB/IEC and Health Authorities, where required, it cannot be implemented.

### **14.1 Protocol amendments**

Any change or addition to the protocol can only be made in a written protocol amendment that must be approved by Novartis Institutes for BioMedical Research, health authorities where required, and the IRB/IEC prior to implementation.

Only amendments that are required for participant safety may be implemented immediately provided the health authorities are subsequently notified by protocol amendment and the reviewing IRB/IEC is notified.

Notwithstanding the need for approval of formal protocol amendments, the Investigator is expected to take any immediate action required for the safety of any participant included in this study, even if this action represents a deviation from the protocol. In such cases, Novartis should be notified of this action and the IRB/IEC at the study site should be informed according to local regulations.

## 16 Appendices

### 16.1 Appendix 1: Liver event and laboratory trigger definitions & follow-up requirements

**Table 16-1 Liver event and laboratory trigger definitions**

	Definition/ threshold
Liver laboratory triggers	
 
ALT or AST > 5 × ULN
 

If ALT, AST and total bilirubin normal at baseline:	
 
ALP > 2 × ULN (in the absence of known bone pathology)
 
Total bilirubin > 3 × ULN (in the absence of known Gilbert syndrome)
 
ALT or AST > 3 × ULN and INR > 1.5
 
Potential Hy's Law cases (defined as ALT or AST > 3 × ULN and Total bilirubin > 2 × ULN [mainly conjugated fraction] without notable increase in ALP to > 2 × ULN)
 
Any clinical event of jaundice (or equivalent term)
 
ALT or AST > 3 × ULN accompanied by (general) malaise, fatigue, abdominal pain, nausea, or vomiting, or rash with eosinophilia
 
Any adverse event potentially indicative of a liver toxicity*
 

If ALT or AST abnormal at baseline:	
 
ALT or AST > 2x baseline or > 300 U/L (whichever occurs first)
 

\*These events cover the following: hepatic failure, fibrosis and cirrhosis, and other liver damage-related conditions; non-infectious hepatitis; benign, malignant and unspecified liver neoplasms ULN: upper limit of normal

**Table 16-2 Follow up requirements for liver laboratory triggers with liver symptoms**

	ALT	TBL	Liver Symptoms	Action
ALT increase without bilirubin increase:				
	
If normal at baseline: ALT > 3 x ULN
 
If elevated at baseline: ALT > 2 x baseline or > 300 U/L (whichever occurs first)
	
Normal
 
For patients with Gilbert's syndrome: No change in baseline TBL
	None	
 
• No change to study treatment
 
• Measure ALT, AST, ALP, GGT, TBIL, INR, albumin, CK, and GLDH in 48-72 hours.
 
• Follow-up for symptoms.
 

	
If normal at baseline: ALT > 5 x ULN for more than two weeks
 
If elevated at baseline: ALT > 3 x baseline or > 300 U/L (whichever occurs first) for more than two weeks
	
Normal
 
For patients with Gilbert's syndrome: No change in baseline TBL
	None	
 
• Interrupt study drug
 
• Measure ALT, AST, ALP, GGT, TBIL, INR, albumin, CK, and GLDH in 48-72 hours.
 
• Follow-up for symptoms.
 
• Initiate close monitoring and workup for competing etiologies.
 

	
If normal at baseline: ALT > 8 x ULN
	Normal	None	

	ALT	TBL	Liver Symptoms	Action
ALT increase with bilirubin increase:				
	
If normal at baseline: ALT > 3 x ULN
 
If elevated at baseline: ALT > 2 x baseline or > 300 U/L (whichever occurs first)
	
TBL > 2 x ULN (or INR > 1.5)
 
For patients with Gilbert's syndrome: Doubling of direct bilirubin
	None	
 
Study drug can be restarted only if another etiology is identified and liver enzymes return to baseline.
 

	
If normal at baseline: ALT > 3 x ULN
 
If elevated at baseline: ALT > 2 x baseline or > 300 U/L (whichever occurs first)
	Normal or elevated	Severe fatigue, nausea, vomiting, right upper quadrant pain	

**Table 16-3 Follow up requirements for liver laboratory triggers**

Criteria	Actions required	Follow-up monitoring
Total Bilirubin (isolated)		
>1.5 – 3.0 ULN	
 
Maintain treatment
 
Repeat LFTs within 48-72 hours
 
	Monitor LFTs weekly until resolution c to ≤ Grade 1 or to baseline
> 3 - 10 × ULN (in the absence of known Gilbert syndrome)	
 
Interrupt treatment
 
Repeat LFT within 48-72 hours
 
Hospitalize if clinically appropriate
 
Establish causality
 
Record the AE and contributing factors (e.g. conmeds, med hx, lab) in the appropriate CRF
 
	Monitor LFTs weekly until resolution c to ≤ Grade 1 or to baseline (ALT, AST, total bilirubin, Alb, PT/INR, ALP and GGT) Test for hemolysis (e.g. reticulocytes, haptoglobin, unconjugated [indirect] bilirubin)
> 10 x ULN	
 
Discontinue the study treatment immediately
 
Hospitalize the participant
 
Establish causality
 
Record the AE and contributing factors(e.g. conmeds, med hx, lab)in the appropriate CRF
 
	ALT, AST, total bilirubin, Alb, PT/INR, ALP and GGT until resolution c (frequency at investigator discretion)
Any AE potentially indicative of a liver toxicity*	
 
Consider study treatment interruption or discontinuation
 
Hospitalization if clinically appropriate
 
Establish causality
 
Record the AE and contributing factors(e.g., conmeds, med hx, lab)in the appropriate CRF
 
	Investigator discretion

aElevated ALT/AST > 3 × ULN and TBL > 2 × ULN but without notable increase in ALP to > 2 × ULN

b(General) malaise, fatigue, abdominal pain, nausea, or vomiting, or rash with eosinophilia

cResolution is defined as an outcome of one of the following: (1) return to baseline values, (2) stable values at three subsequent monitoring visits at least 2 weeks apart, (3) remain at elevated level after a maximum of 6 months, (4) liver transplantation, and (5) death.

Based on Investigator’s discretion investigation(s) for contributing factors for the liver event can include: Serology tests, imaging and pathology assessments, hepatologist’s consultancy; obtaining more detailed history of symptoms and prior or concurrent diseases, history of concomitant drug use, exclusion of underlying liver disease.

## 16.2 Appendix 2: Specific Renal Alert Criteria and Actions and Event Follow-up

**Table 16-4 Specific Renal Alert Criteria and Actions**

Renal Event	Actions
Confirmed serum creatinine increase 25-49%	
 
Consider causes and possible interventions
 
Follow up within 2-5 days
 

Serum creatinine increase $\geq 50\%$	
 
Consider causes and possible interventions
 
Repeat assessment within 24-48 h if possible
 
Consider drug interruption or discontinuation unless other causes are diagnosed and corrected
 
Consider patient hospitalization and specialized treatment
 

New onset dipstick proteinuria $\geq 3+$ OR Protein-creatinine ratio (PCR) $\geq 1\text{g/g Cr}$ (or mg/mmol equivalent as converted by the measuring laboratory)	
 
Consider causes and possible interventions
 
Assess serum albumin & serum total protein
 
Repeat assessment to confirm
 
Consider drug interruption or discontinuation unless other causes are diagnosed and corrected
 

New onset hematuria $\geq 3+$ on urine dipstick	
Assess & document:
 
 
Repeat assessment to confirm
 
Distinguish hemoglobinuria from hematuria
 
Urine sediment microscopy
 
Assess sCr
 
Exclude infection, trauma, bleeding from the distal urinary tract/bladder, menstruation
 
Consider bleeding disorder
 

**Table 16-5 Renal Event Follow Up**

Follow-up of Renal Events

Assess, document, and record in eCRF:
 
 
Urine dipstick and sediment microscopy evidence of DIN: crystals, red blood cells (dysmorphic/glomerular vs. non-dsymophic/non-glomerular), white blood cells, tubular epithelial cells
 
Blood pressure and body weight
 
Serum creatinine, BUN, electrolytes (sodium, potassium, phosphate, calcium), bicarbonate, and uric acid
 
Urine output
 

Review and record possible contributing factors to the renal event (co-medications, other co-morbid conditions) and additional diagnostic procedures (MRI etc.) in the eCRF

Monitor patient regularly (frequency at investigator's discretion) until:
 
 
Event resolution (sCr within 10% of baseline or PCR <math>< 1\text{g/g Cr}</math>, or ACR <math>< 300\text{ mg/g Cr}</math>) or
 
Event stabilization: sCr level with <math>\pm 10\%</math> variability over last 6 months or protein-creatinine ratio stabilization at a new level with <math>\pm 50\%</math> variability over the last 6 months.
 
Analysis of urine markers in samples collected over the course of the DIN event
 

1.1 Scope of document

The RAP documents contain detailed information to aid the production of Statistics & Programming input into the Clinical Study Report (CSR) CCI for trial CHSY244X2201.

The Statistical analysis plan (SAP) describes the implementation of the statistical analysis planned in the protocol.

1.2 Study reference documentation

The study protocol (v04) was available at the time of finalization of this Statistical Analysis Plan Amendment 1.

| Objective(s) | Endpoint(s) | | | |
|--|---|--|--|--|
| Primary objective(s) | Endpoint(s) for primary objective(s) | | | |
| • To evaluate the efficacy of HSY244 to restore sinus rhythm in participants with AF | • Conversion to sinus rhythm for at least 1 minute within 90 minutes from the start of study drug administration | | | |
| Secondary objective(s) | Endpoint(s) for secondary objective(s) | | | |
| • To evaluate the safety and tolerability of HSY244 in participants with AF | • Results of safety assessments including adverse events, vital signs, ECG parameters, and laboratory assessments of blood and urine. | | | |
| • To evaluate the pharmacokinetics of HSY244 in participants with AF | • HSY244 plasma AUClast, Cmax, and Tmax after i.v. administration | | | |
| Exploratory objective(s) | Endpoint(s) for exploratory objective(s) | | | |
| Commercially Confidential Information | | | | |

1.3 Study objectives

| Novartis SAP | For business use only | Page 5 CHSY244X2201 |
|-----------------|-----------------------|------------------------|
| | | |

Objective(s)

Commercially Confidential Information

Endpoint(s)

1.4 Study design and treatment

This is a randomized, placebo-controlled, investigator- and participant-blinded study to evaluate the efficacy, safety, tolerability, and pharmacokinetics of HSY244 in participants with AF. An initial cohort (Cohort 1) of approximately 29 participants (approximately 20 participants receiving HSY244) is planned to be enrolled to evaluate a single 150 mg i.v. dose of HSY244 for AF cardioversion to sinus rhythm.

Commercially Confidential Information

Participants with AF that meet clinical criteria for direct current cardioversion will be screened, and on Day 1, after eligibility is confirmed, administration of a 15 minute i.v. infusion of HSY244 or placebo will occur. Participants will then be monitored for cardioversion to sinus rhythm. For those remaining in AF after 90 minutes, direct current cardioversion can be performed. Participants will be monitored for at least 3 hours, although overnight observation will be available. Participants will be evaluated for safety and pharmacokinetic assessments during end of study assessments, which are to occur on Day 5 (96 hours post dose) \pm 24 hours.

2 First interpretable results (FIR)

First interpretable results (FIR) will be provided for this trial. Commercially Confidential Information

The FIR will focus on the following analyses:

- 1. Participant Disposition
- 2. Demographics and baseline characteristics by cohort. Baseline characteristics include, but not limited to: age, sex, race, ethnicity, BMI, relevant medical history/current medical conditions (previous diagnosis of heart failure, etc.), duration of current AF episode, etc.
- 3. Safety Results
 - a. Number and percentage of adverse events by body system and Cohort
 - b. Number and percentage of adverse events by preferred term and Cohort
- 4. Pharmacokinetic results for each Cohort
- 5. Pharmacodynamic analyses include, but are not limited to:
 - a. Fisher's exact test comparing conversion rates between HSY244 and placebo
 - b. MMRM analysis of ECG and heart rate parameters comparing HSY244 and placebo
 - c. Concentration effect analysis of QT and Heart Rate parameters
 - d. Time to event analysis for the time to conversion and time in sinus rhythm after conversion comparing HSY244 and placebo
 - e. AF burden comparison between HSY244 and placebo

3 Interim analyses

4 Statistical methods: Analysis sets

For all analysis sets, participants will be analyzed according to the study treatment(s) received.

The safety analysis set will include all participants that received any investigational product.

The PK analysis set will include all participants with at least one available valid PK concentration measurement, who received any investigational product and with no protocol deviations that impact on PK data.

Commercially Confidential Information

The analysis sets and protocol deviation codes are related as follows:

 Table 4-1
 Protocol deviation codes and analysis sets Commercially Confidential Information
 If updates to Table 4-1 are needed, an amendment to the SAP needs to be implemented prior to DBL.

5 Statistical methods for Pharmacokinetic (PK) parameters

All participants within the PK analysis set will be included in the PK data analysis.

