#### Figure 3-1 Study Design

Commercially Confidential Information

For Cohort 1 CCI the following will occur:

A screening period of up to 3 days (72 hours) will be used to assess eligibility. After eligibility is confirmed, participants will be randomized to either HSY244 or placebo. Prior to study drug administration, pre-dose assessments will be completed (refer to [Section 8](#) for complete details). Standard clinical care practices should be followed per Investigator's discretion, including but not limited to bedside telemetry and application of defibrillator pads. A study 12-lead Holter (continuous ECG) monitor will be applied for continuous heart rate and rhythm monitoring for 24 hours and will also allow for single-timepoint ECG tracings to be captured. After the participant's ongoing AF episode is confirmed, study drug administration of a 15 minute i.v. infusion of HSY244 or placebo will begin; this is time '0' as related to all post-dose assessments. After the start of study drug administration, the participant will be monitored for cardioversion to sinus rhythm. If a participant is still in AF at 90 minutes after the start of study drug administration, direct current cardioversion may be applied at a time deemed appropriate by the investigator. Standard clinical care approaches should be followed for direct current

cardioversion but alternatives should be considered for the medications on the prohibited medication list (Table 6-2) until the EOS visit has occurred.

For the first 120 minutes (2 hours) after study drug administration, the participant should be resting in the supine or semi-recumbent position with minimal disturbances to allow for assessments of heart rate CCI. If direct current cardioversion is applied at 90 minutes, there should be an additional 30 minutes afterward during which the participant should be resting in the supine or semi-recumbent position with minimal disturbances to allow for assessments of heart rate CCI.

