The participant should be monitored for at least 180 minutes (3 hours), after study drug administration for safety and blood sampling; this monitoring period can be extended through 24 hours if deemed necessary or appropriate by the Investigator and/or for convenience for the participant. The participant can be transferred to other locations within the study site (i.e., to a post-anesthesia care unit [PACU], hospital ward, or clinical trials unit given site staff is appropriately trained) during the 3 hour monitoring period (or for 24 hours if observation period is extended), at the discretion of the Investigator, as long as the participant can remain undisturbed (i.e., remain in supine/semi-recumbent position for the first 2 hours), and the study protocol requirements, assessments and appropriate standard clinical care practices are possible.

Commercially Confidential Information

If the participant remains on-site overnight, Day 2 (24 hours post-dose) assessments should be completed before the participant's release from the study site. If the participant does not remain at the site overnight, the site will call the participant on Day 2 (24 hours post dose  $\pm$ 4 hours) to check on AEs, as well as to guide the participant for the removal of the Holter device. The participant should remain resting in a supine or semi-recumbent position for at least 15 minutes prior to the removal of the Holter (continuous ECG) monitor to allow for the assessment of resting heart rate CCI. The participant is required to return to the study site within  $\pm$ 24 hours of Day 5 (96 hours post dose) for end of study (EOS) assessments.

A total of approximately 29 participants are planned to be randomized in Cohort 1, of which approximately 20 will receive HSY244. Participants will be randomized in a 5:1 HSY244-to-placebo ratio.

Commercially Confidential Information

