## 5 Study Population

The study population will include hemodynamically stable men and women between 18 and 80 years of age with a clinical indication for direct current cardioversion of AF, with the current AF episode lasting between 6 hours and 60 days. In Cohort 1, a total of approximately 29 participants with AF will be randomized, of which approximately 20 will receive HSY244.

Commercially Confidential Information

Replacement participants will be allowed for those participants who discontinue study drug administration before completion if those participants have not discontinued due to adverse drug reactions or adverse events from study procedures. A maximum of 4 replacement participants will be allowed per Cohort. Please refer to [Section 9.2](#) for additional details. Rescreening of screen failures will be allowed. Please refer to [Section 8.1](#) for additional details.

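### SAP item 5d compares the arms on time in sinus rhythm after conversion, which as worded exists only for converters, so the comparison selects on a post-randomization outcome

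*SAP*

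**What the plan says.** SAP section 2 lists what the first interpretable results will contain. Item 5d reads "Time to event analysis for the time to conversion and time in sinus rhythm after conversion comparing HSY244 and placebo". It covers two quantities: time to conversion, and the one at issue here, "time in sinus rhythm after conversion comparing HSY244 and placebo". The next line, item 5e, lists an arm comparison of AF burden.

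The conversion event is the primary endpoint: "Conversion to sinus rhythm for at least 1 minute within 90 minutes from the start of study drug administration" (SAP 1.2). After that window the rhythm can be changed by a shock: "For those remaining in AF after 90 minutes, direct current cardioversion can be performed" (SAP 1.4). Rhythm is recorded well beyond 90 minutes, since a Holter "monitor will be applied for continuous heart rate and rhythm monitoring for 24 hours" (Protocol section 3). Protocol 8.3.1 says that central reading covers both cardioversion and AF burden.

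On numbers, Protocol section 3 states "A total of approximately 29 participants are planned to be randomized in Cohort 1, of which approximately 20 will receive HSY244" and "Participants will be randomized in a 5:1 HSY244-to-placebo ratio". SAP 6.1.3 analyzes cohorts separately and leaves pooling of placebo across cohorts as an option. SAP 6.2 says that there are no secondary PD objectives. The exploratory methods (SAP 6.3.1 to 6.3.4, Protocol 12.6) and the sample size section (Protocol 12.8.1) are redacted.

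**The concern.** A duration that begins at conversion has no starting point in someone who never converts. If only converters enter the analysis, membership is decided after randomization by the outcome that HSY244 is intended to produce. Placebo converters convert spontaneously. HSY244 converters are a mixture of participants who would have converted anyway and participants who converted because of the drug. The two groups can differ in how long they hold sinus rhythm even if the drug has no effect on maintenance, and randomization does not protect against that.

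This matters because the primary endpoint asks for only one minute of sinus rhythm. How long it lasts is the next question any reader will ask, and item 5d looks like the answer. An early result that shows HSY244 converters relapsing sooner or later than placebo converters could be read as a drug effect on durability when it reflects only who converted. A placebo arm this small adds a second problem: there may be nobody, or one person, to compare with.

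**Working it through.** **Step 1. Who has a value for each quantity.**

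| Quantity | Clock starts | Defined for |
|---|---|---|
| Time to conversion (5d, first part) | Start of dosing | Everyone treated |
| Time in sinus rhythm after conversion (5d, second part) | Conversion | Converters only, as worded |
| AF burden (5e) | Not visible | Can be defined for everyone treated |

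Only the second row selects on a post-randomization outcome.

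**Step 2. What selection alone can do (all inputs assumed).** Suppose 10% of participants convert in either arm and hold sinus rhythm for a mean of 20 hours. A further 40% convert only with the drug and hold it for a mean of 12 hours. The drug has no effect on maintenance in anyone.
- Placebo converters: mean 20 hours.
- HSY244 converters: (0.10 × 20 + 0.40 × 12) / 0.50 = 6.8 / 0.50 = 13.6 hours.

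The 6.4-hour gap comes entirely from who converts. With splits of 5% / 45% and 20% / 30%, the HSY244 mean is 12.8 and 15.2 hours. The direction is a product of these assumptions and could be reversed. The example shows only that a gap can arise without any drug effect.

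**Step 3. How many are on placebo.** The stated figures do not reproduce one another:
- 29 at 5:1 gives 29 / 6 = 4.8 placebo and 24.2 active.
- 20 active at 5:1 gives 20 / 5 = 4 placebo, 24 in total.
- 29 − 20 = 9 placebo, a ratio of 20 / 9 = 2.2:1.

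The replacement rule, "A maximum of 4 replacement participants will be allowed per Cohort" (Protocol section 5), brings 24 up to 28. That is near 29, but the visible text does not offer it as the explanation. The working range is therefore 4, 5 or 9.

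**Step 4. How many placebo converters.** The visible text gives no placebo conversion rate *p*, so it is varied. With *n* on placebo, P(at most one converter) = (1 − p)^n + n·p·(1 − p)^(n−1). For n = 5 and p = 10%: 0.9^5 + 5 × 0.1 × 0.9^4 = 0.590 + 0.328 = 0.919 after rounding.

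| Placebo n | 5% | 10% | 20% | 30% | Exceeds 50% up to p of about |
|---|---|---|---|---|---|
| 4 | 98.6% | 94.8% | 81.9% | 65.2% | 39% |
| 5 | 97.7% | 91.9% | 73.7% | 52.8% | 31% |
| 9 | 92.9% | 77.5% | 43.6% | 19.6% | 18% |
| 8 (two pooled cohorts of 4) | 94.3% | 81.3% | 50.3% | 25.5% | 20% |
| 10 (two pooled cohorts of 5) | 91.4% | 73.6% | 37.6% | 14.9% | 16% |
| 18 (two pooled cohorts of 9) | 77.4% | 45.0% | 9.9% | 1.4% | 9% |

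The pooled rows assume a second cohort of equal size, since its size is redacted. The chance of no placebo converter at 5%, 10% and 20% is 81.5%, 65.6% and 41.0% for n = 4; 77.4%, 59.0% and 32.8% for n = 5; and 63.0%, 38.7% and 13.4% for n = 9.

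**Step 5. What one placebo converter allows.** Against *m* HSY244 converters, the smallest two-sided rank p-value is 2 / (m + 1). With an assumed m = 10 this is 2 / 11 = 0.18, however extreme the single placebo value is.

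**The case against.** The strongest reply is that item 5d is one line in a summary list and the method behind it is redacted. SAP 6.3 may give non-converters a duration of zero, may say how sinus rhythm after a shock counts, or may limit the analysis to description. That stands. A reader might infer that the plan has no handling for non-converters, but the documents do not support this. What can be said is that the visible wording describes a quantity defined only after conversion and attaches an arm comparison to it.

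A second reply is that item 5e already offers a comparison that can include everyone. This also stands, and it shapes the remedy. It does not dispose of the point, because item 5d remains listed beside it, and the window for AF burden and its treatment of shocks are not visible.

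Third, a reader might infer that the comparison will usually rest on no placebo participant or one. The documents do not support that without conditions. They give no placebo rate, the placebo count could be 9, and pooling is permitted. At 20% with 9 on placebo the chance is 43.6%, which is less than even.

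Fourth, the analysis is evidently exploratory. The primary objective rests on Fisher's exact test of conversion, and no visible decision depends on item 5d. That limits the consequence to how early results are read.

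**Conclusion.** The second half of item 5d, as worded, is not a comparison of the randomized arms. That conclusion follows from where the clock starts. It needs no assumption about sample size or conversion rate, and pooling placebo would not cure it. The first half, time to conversion, is unaffected, and so is the primary analysis.

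The sparsity is a second, conditional weakness. With 4 or 5 on placebo, at most one placebo converter is the likelier outcome for any placebo rate up to about 39% or 31%. With 9 it is the likelier outcome only up to about 18%, and with 18 pooled only up to about 9%. These statements rest on assumed rates, and for the pooled case on an assumed second cohort.

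This is a minor point about an exploratory line, worth correcting because the change is small. If SAP 6.3 already counts non-converters or confines the analysis to description, only the wording of item 5d needs to change.

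**What to change.** Amend SAP section 2 and, where needed, the matching text in SAP 6.3:

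- **Keep** the between-arm comparison of time to conversion.
- **Make time in sinus rhythm after conversion descriptive.** Give the number of converters per arm, a Kaplan-Meier curve with 80% CI for HSY244 converters, and an individual listing for any placebo converters. Draw no between-arm inference.
- **Use item 5e for the between-arm rhythm comparison.** Analyze AF burden in all treated participants, non-converters included. Show the 0 to 90 minute window separately, because it precedes planned direct current cardioversion. Say how rhythm after a shock is handled in any longer window.
- **Do not present the 0 to 90 minute result as durability.** It mixes whether, when and for how long sinus rhythm occurs: a participant who converts at 80 minutes can contribute at most 90 − 80 = 10 minutes of sinus rhythm to that window.
- **Reconcile 29, 20 and 5:1**, so that the number on placebo is known.

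The cost is a short SAP edit and one listing, from Holter data that are already read centrally. The plan gives up a formal arm comparison of durability after conversion, which this design could not validly support. The AF burden comparison removes the selection but not the small numbers: it would rest on 4 to 9 placebo participants, or more if cohorts are pooled.
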